7.1.1 Rechallenge

Rechallenge with Olaparib in this study is not allowed. Due to adverse events, the maximum dose can be reduced to 200 mg BD as per section 8.4.6. However, if drug discontinuation is necessary, the subject shall not be restarted on Olaparib subsequently.

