Palliative radiotherapy may be used for the treatment of pain at the site of bony metastases that were present at baseline, provided the investigator does not feel that these are indicative of clinical disease progression during the study period. Study treatment should be discontinued for a minimum of 3 days before a patient undergoes therapeutic palliative radiation treatment. Study treatment should be restarted within 4 weeks as long as any bone marrow toxicity has recovered.

Administration of other anti-cancer agents

Patients must not receive any other concurrent anti-cancer therapy, including investigational agents, while on study treatment. Patients may continue the use of bisphosphonates or denosumab for bone disease and corticosteroids for the symptomatic control of brain metastases provided the dose is stable before and during the study and they were started at least 4 weeks prior to beginning study treatment.

Other concomitant treatment

Other medication other than that described above, which is considered necessary for the patient's safety and wellbeing, may be given at the discretion of the Investigator and recorded in the appropriate sections of the Case Report Form.

In addition, any unplanned diagnostic, therapeutic or surgical procedure performed during the study period must be recorded in the eCRF.

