6.6 Dose modification

This protocol allows for some alteration from the currently outlined dosing schedule, but the maximum daily dose shall not exceed 300 mg BD. Dose modifications are permitted in case of AE's as per section 8.4.6.

In case a dose reduction is necessary, the Study treatment will be administered as follows:

Table 5: Dose Reduction Schedule

Initial dose	Following re-challenge post interruption: Dose reduction 1	Dose reduction 2
300 mg twice daily	250 mg Twice daily	200 mg twice daily (lowest allowable dose level)

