8.4.5.2 Management of neutropenia, leukopenia and thrombocytopenia

Table 8 Management of neutropenia, leukopenia and thrombocytopenia

Toxicity	Study treatment dose adjustment
CTCAE Grade 1-2	Investigator judgement to continue treatment or if dose interruption, this should be for a maximum of 4 weeks; appropriate supportive treatment and causality investigation
CTCAE Grade 3-4	Dose interruption until recovered to CTCAE gr 1 or better for a maximum of 4 weeks. If repeat CTCAE grade 3-4 occurrence, dose reduce to 250 mg twice daily as a first step and 200 mg twice daily as a second step

Adverse event of neutropenia and leukopenia should be managed as deemed appropriate by the investigator with close follow up and interruption of study drug if CTC grade 3 or worse neutropenia occurs.

Primary prophylaxis with Granulocyte colony-stimulating factor (G-CSF) is not recommended, however, if a subject develops febrile neutropenia, study treatment should be stopped and appropriate management including G-CSF should be given according to local hospital guidelines. Please note that G-CSF should not be used within at least 24 h (7 days for pegylated G-CSF) of the last dose of study treatment unless absolutely necessary.

Platelet transfusions, if indicated, should be done according to local hospital guidelines.

For cases where subjects develop prolonged haematological toxicity (\geq 2 weeks interruption/delay in study treatment due to CTC grade 3 or worse), refer to Section 8.4.5.3.

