8.4.6 Management of Non – hematological toxicity

Repeat dose interruptions are allowed as required, for a maximum of 4 weeks on each occasion. If the interruption is any longer than this the study monitor must be informed. Where toxicity reoccurs following re-challenge with study treatment, and where further dose interruptions are considered inadequate for management of toxicity, then the subject should be considered for dose reduction or must permanently discontinue study treatment.

Study treatment can be dose reduced to 250 mg bd as a first step and to 200 mg bd as a second step. Treatment must be interrupted if any NCI-CTCAE grade 3 or 4 adverse event occurs which the investigator considers to be related to administration of study treatment.

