8.4.6.3 Interruptions for intercurrent non-toxicity related events

Study treatment dose interruption for conditions other than toxicity resolution should be kept as short as possible. If a subject cannot restart study treatment within 4 weeks for resolution of intercurrent conditions not related to disease progression or toxicity, the case should be discussed with AZ study physician.

All dose reductions and interruptions (including any missed doses), and the reasons for the reductions/interruptions are to be recorded in the eCRF.

Study treatment should be stopped at least 3 days prior to planned surgery. After surgery study treatment can be restarted when the wound has healed. No stoppage of study treatment is required for any needle biopsy procedure.

Study treatment should be discontinued for a minimum of 3 days before a subject undergoes radiation treatment. Study treatment should be restarted within 4 weeks as long as any bone marrow toxicity has recovered.

Because the AEs related to olaparib may include asthenia, fatigue and dizziness, subjects should be advised to use caution while driving or using machinery if these symptoms occur. For the dose reduction schedule, please refer to Table 5: Dose Reduction Schedule

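### Section 7.1.1 bans rechallenge and any restart after discontinuation, but the dose-reduction, toxicity and radiotherapy sections rely on both, so sites may handle and classify the same stop differently

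*Protocol*

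**What the plan says.** Section 7.1.1 opens with "Rechallenge with Olaparib in this study is not allowed". It then allows the dose to be lowered under 8.4.6, and closes with "However, if drug discontinuation is necessary, the subject shall not be restarted on Olaparib subsequently".

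Other sections describe treatment being paused and resumed:

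- **6.6, Table 5.** The first reduced dose level is headed "Following re-challenge post interruption: Dose reduction 1".
- **8.4.6.** The rule for non-haematological toxicity begins "Where toxicity reoccurs following re-challenge with study treatment" and allows repeated interruptions.
- **6.5.1, palliative radiotherapy.** "Study treatment should be discontinued for a minimum of 3 days before a patient undergoes therapeutic palliative radiation treatment". The next sentence has treatment resumed inside 4 weeks once any marrow toxicity has resolved.
- **8.4.6.3.** "Study treatment should be discontinued for a minimum of 3 days before a subject undergoes radiation treatment", with the same resumption rule. For planned surgery this section says treatment is stopped and may resume after wound healing.
- **8.4.5.2.** "if a subject develops febrile neutropenia, study treatment should be stopped", with no statement about restarting. Table 8 in the same section interrupts for grade 3-4 events until recovery, and adds "If repeat CTCAE grade 3-4 occurrence, dose reduce to 250 mg twice daily as a first step".

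The protocol does not define rechallenge. It also has no general definition separating a temporary from a permanent discontinuation.

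**The concern.** The ban in 7.1.1 is absolute, yet the section it cites for dose reduction contains the step it bans. The final sentence of 7.1.1 bars restart after discontinuation, while two other sections use that word for a pause that must end in a restart. A site that follows 7.1.1 to the letter could end treatment where a site that follows 8.4.5 or 8.4.6 would hold and resume.

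This matters because the study is single-arm, planned for 15 sites, and has AE occurrence as its primary endpoint. How long a subject stays on drug, and whether a stop counts as a discontinuation, both feed into which AEs are collected and reported. If sites read the rules differently, part of the observed safety profile reflects site interpretation, and there is no control arm to show how much.

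**Working it through.** The point is textual, so the check sets the passages side by side. The protocol's one statistical figure is not at issue and reproduces. With p = 0.40, margin 0.07 and a 95% interval (section 9.2), n = 1.96² × 0.40 × 0.60 / 0.07² ≈ 188.2, rounded up to 189, against the stated approximately 190.

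**Step 1: rechallenge.** 7.1.1 bans it. Table 5 and 8.4.6 presuppose it after an interruption. 8.4.6.1 also allows a restart after an interruption for pulmonary symptoms. The nearest thing to a definition is the causality guide in Appendix B 7, which treats re-challenge as reintroducing a drug that had been stopped. That is broad enough to include resuming after a hold. Read literally, 7.1.1 and 8.4.6 cannot both be followed.

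**Step 2: the narrower reading.** Suppose 7.1.1 means only that nobody restarts after *permanent* discontinuation. The text does not say so. Even then, 6.5.1 and 8.4.6.3 call the pre-radiation pause a discontinuation and require a restart, so the word still carries two meanings.

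**Step 3: *stopped*.** For surgery it means pause and resume (8.4.6.3). For febrile neutropenia it has no restart rule (8.4.5.2), beside a table that interrupts until recovery. A site cannot tell from the text which meaning applies.

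**Step 4: the boundary in time.** Section 7.1 makes a related-AE hold of more than 21 days permanent. Sections 8.4.5 and 8.4.6 allow interruptions of up to 4 weeks, which is 28 days. The difference is 28 − 21 = 7 days, so the point at which a hold becomes a discontinuation is not fixed either.

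**Step 5: what depends on the classification.**

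- *Phase.* Under 4.1, discontinuing the drug during the Treatment Phase starts the Follow-up Phase.
- *AE window.* Under 8.3.2 and 9.4.2, collection and summaries run to 28 days after the last dose. As an illustration, take a subject whose last dose is on Day 57, a scheduled visit day. Her window closes on Day 57 + 28 = Day 85. Had she resumed and stayed on treatment, she would have been observed to at least Day 182, which is 182 − 85 = 97 days longer.
- *Laboratory AEs.* Under 8.3.7, a deterioration in a protocol-mandated laboratory value is an AE only if it meets a seriousness criterion or is the reason for discontinuing. An asymptomatic, non-serious fall that leads to a stop could be an AE at a site that calls the stop a discontinuation and go unreported at a site that calls it an interruption.

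**Step 6: what the data would show.** Section 6.4 lists interruptions, reductions and discontinuations as separate eCRF entries. Section 8.4.6.3 requires reasons for interruptions and reductions, 7.1.2 requires the date of last intake, and 8.3.4 records the action taken with study drug for each AE. The two kinds of stop are therefore distinguishable in the database, as the site classified them. What remains is variation in how sites act and classify.

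**The case against.** The strongest reply is that 7.1.1 is being read against its context. It sits under the heading on discontinuation. Its second sentence allows dose reduction under 8.4.6, and its last sentence begins with a contrast between that and discontinuation. Section 7.1 itself recognises holds of up to 3 weeks. Most sites would probably infer that only permanent stops are covered. The radiotherapy wording names a minimum of 3 days and a restart, and in 8.4.6.3 it stands under a heading about interruptions, so few would take it as permanent. This makes the most literal reading less likely, but the ban remains unqualified and the terms undefined. Nor does it resolve the febrile neutropenia wording.

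The effect on AE incidence also has limits. A subject whose grade 3 or higher AE prompts a hold already counts towards that incidence. Symptoms that accompany a laboratory change are reported in any case (8.3.7). Anaemia or neutropenia needing transfusion is an Appendix B 5 example of an important medical event. Section 7.1.2 asks discontinued subjects to keep attending visits, although AE collection is still tied to 28 days after the last dose.

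Three stronger readings are tempting and are not supported:

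- *Permanent stops and interruptions cannot be told apart.* The separate eCRF entries contradict this.
- *The 40% planning rate in 9.2 implies up to 0.40 × 200 = 80 forced discontinuations, against about 0.049 × 200 ≈ 10 at the rate quoted for the breast cancer trial.* This needs every site to take the most literal reading. The 40% also counts labelled grade 3 or higher events whether related or not, while 8.4.6 mandates interruption only for related ones. The protocol gives no related share.
- *Table 5 contradicts Tables 7 and 8 on when the first reduction applies.* Table 5 is introduced as applying once a reduction is needed, so it can be read as a list of dose levels, with the other tables giving the triggers. Its column heading is unclear, but a contradiction is not established.

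**Conclusion.** The contradiction is real as written. 7.1.1 cannot be followed literally together with Table 5 and 8.4.6, and its bar on restart clashes with the wording for radiation in 6.5.1 and 8.4.6.3. *Stopped* is used with two meanings. Sites may therefore handle and classify the same stop differently. The consequences reach a subject's continued treatment, her entry to follow-up, the closing of her AE window and the reporting of some laboratory deteriorations.

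No overall size can be given. It depends on how many sites read 7.1.1 literally and how many subjects have a qualifying hold, and the protocol supplies neither. The 97 days above describe one assumed subject and are not an estimate for the trial. The conclusion assumes only that sites act on the text as it stands, without further written instruction.

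**What to change.** The sponsor should reconcile 7.1.1 with Table 5, 8.4.5, 8.4.6, 8.4.6.3 and 6.5.1, with the clinical team deciding which rule applies in each case. This review takes no position on that choice.

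- Define two terms once: *interruption* (restart possible under the stated rules) and *permanent discontinuation* (no restart).
- Use only those terms in place of *discontinued*, *stopped* and *rechallenge*. This includes the passages on radiotherapy, surgery and febrile neutropenia.
- Reconcile the 21-day limit in 7.1 with the 4-week limits in 8.4.5 and 8.4.6, so that the boundary between the two terms is fixed.
- Clarify Table 5's column heading so that it agrees with the triggers in Tables 7 and 8.
- Use the same two terms in the eCRF field for action taken with study drug.

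The cost is amendment wording and alignment of one eCRF code list. No extra visits or subjects are needed.

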7.1.2 Procedures for discontinuation of study treatment

The investigator should instruct the subject to contact the site before or at the time if Study treatment is stopped. A subject that decides to discontinue Study treatment will always be asked about the reason(s) and the presence of any AEs. The date of last intake of Study treatment should be documented in the eCRF. All Study treatment should be returned by the subject at their next on-site study visit or unscheduled visit. Subjects permanently discontinuing Study treatment should be given locally available standard of care therapy, at the discretion of the Investigator.

Discontinuation of Study treatment, for any reason, does not impact on the subject's participation in the study. The subject should continue attending subsequent study visits and data collection should continue according to the study protocol. If the subject does not agree to continue in-person study visits, a modified follow-up must be arranged to ensure the collection of endpoints and safety information. This could be a telephone contact with the subject at 28 days post discontinuation

(End of Study Visit as described in SoA), a contact with a relative or treating physician, or information from medical records. The approach taken should be recorded in the medical records. A subject that agrees to modified follow-up is not considered to have withdrawn consent or to have withdrawn from the study.

7.2 Lost to follow-up

A subject will be considered potentially lost to follow-up if he or she fails to return for scheduled visits and is unable to be contacted by the study site.

The following actions must be taken if a subject fails to return to the clinic for a required study visit:

- The site must attempt to contact the subject and reschedule the missed visit as soon as possible and counsel the subject on the importance of maintaining the assigned visit schedule.
- Before a subject is deemed lost to follow up, the investigator or designee must make every effort to regain contact with the subject or next of kin by e.g. repeat telephone calls, certified letter to the subject's last known mailing address or local equivalent methods. These contact attempts should be documented in the subject's medical record.
- Efforts to reach the subject should continue until the end of the study. Should the subject be unreachable at the end of the study, the subject should be considered to be lost to follow up with unknown vital status at end of study and censored at latest follow up contact.

7.3 Withdrawal from the study

A subject may withdraw from the study (e.g., withdraw consent), at any time (study drug **and** assessments) at his/her own request, without prejudice to further treatment.

A subject who considers withdrawing from the study must be informed by the Investigator about modified follow-up options (e.g., telephone contact, a contact with a relative or treating physician, or information from medical records).

If the subject withdraws consent for disclosure of future information, the sponsor may retain and continue to use any data collected before such a withdrawal of consent.

If a subject withdraws from the study, he/she may request destruction of any samples taken, and the investigator must document this in the site study records. A subject who withdraws consent will always be asked about the reason(s) and the presence of any adverse events (AE). The Investigator will follow up subjects as medically indicated.

AstraZeneca or its delegate will request investigators to collect information on subjects' vital status (dead or alive; date of death when applicable) at the EOS visit (Day 182 or 28 days from the date of withdrawal from the study) from publicly available sources, in accordance with local

regulations. Knowledge of the vital status at the EOS visit in all subject is crucial for the integrity of the study.

See SoA, Table 1, for data to be collected at the time of study discontinuation and follow-up and for any further evaluations that need to be completed. All Study treatment should be returned by the subject.

8. STUDY ASSESSMENTS AND PROCEDURES

Study procedures and their timing are summarised in the SoA.

The investigator will ensure that data are recorded on the electronic Case Report Forms

The investigator ensures the accuracy, completeness, for eCRFs include: legibility and timeliness of the data recorded and of the provision of answers to data queries according to the Clinical Study Agreement. The investigator will sign the completed electronic Case Report Forms. A copy of the completed electronic Case Report Forms will be archived at the study site.

Immediate safety concerns should be discussed with the sponsor immediately upon occurrence or awareness to determine if the subject should continue or discontinue Study treatment.

Adherence to the study design requirements, including those specified in the SoA, is essential and required for study conduct.

All screening evaluations must be completed and reviewed to confirm that potential subjects meet all eligibility criteria. The investigator will maintain a screening log to record details of all subjects screened and to confirm eligibility or record reasons for screening failure, as applicable.

Procedures conducted as part of the subject's routine clinical management (e.g., blood count) and obtained before signing of the ICF may be utilised for screening or baseline purposes provided the procedures met the protocol-specified criteria and were performed within the time frame defined in the SoA.

The maximum amount of blood collected from each subject over the duration of the study, including any extra assessments that may be required, will not exceed 10 mL. Repeat or unscheduled samples may be taken for safety reasons or for technical issues with the samples.

8.1 Efficacy assessments

This study does not intend to assess any clinical efficacy outcomes as the study is being conducted as a part of the local regulatory requirement.

8.2 Safety assessments

Planned time points for all safety assessments are provided in the SoA.

8.2.1 Clinical safety laboratory assessments

See Table 6 Laboratory safety variables for the list of clinical safety laboratory tests to be performed and to the SoA for the timing and frequency. All protocol-required laboratory assessments, as defined in the table, must be conducted in accordance with the laboratory manual and the SoA.

The Investigator should assess the available results with regard to clinically relevant abnormalities. The laboratory results should be signed and dated and retained at centre as source data for laboratory variables.

For information on how AEs based on laboratory tests should be recorded and reported, see Section 8.3.7.

Additional safety samples may be collected if clinically indicated at the discretion of the Investigator. The date, time of collection and results (values, units and reference ranges) will be recorded on the appropriate CRF.

The clinical chemistry, haematology and urinalysis will be performed at a local laboratory at or near to the Investigator site. Sample tubes and sample sizes may vary depending on laboratory method used and routine practice at the site.

Table 6 Laboratory safety variables

Haematology/Haemostasis (whole blood)	Clinical Chemistry (serum or plasma)
B-Haemoglobin (Hb)	S/P-Creatinine
B-Leukocyte count	S/P-Bilirubin, total
B-Leukocyte differential count (absolute count)	S/P-Alkaline phosphatase (ALP)
B-Platelet count	S/P-Aspartate transaminase (AST)
	S/P-Alanine transaminase (ALT)
Urinalysis (dipstick)	S/P-Albumin
U-Hb/Erythrocytes/Blood	
U-Protein/Albumin	
U-Glucose	

NB. In case a subject shows an AST or ALT $\geq 3 \times \text{ULN}$ together with total bilirubin $\geq 2 \times \text{ULN}$ please refer to Appendix E 'Actions required in cases of increases in liver biochemistry and evaluation of Hy's Law', for further instructions.

8.2.1.1 Coagulation

Activated partial thromboplastin time (APTT) will be performed at screening and if clinically indicated.

International normalised ratio (INR) will be performed at screening and if clinically indicated. Subjects taking warfarin may participate in this study; however, it is recommended that INR be monitored carefully at least once per week for the first month, then monthly if the INR is stable.

Each coagulation test result will be recorded in eCRF.

8.2.1.2 Bone marrow or blood cytogenetic samples

Bone marrow or blood cytogenetic samples may be collected for subjects with prolonged haematological toxicities as defined in Section 8.4.5.3

Bone marrow analysis should include an aspirate for cellular morphology, cytogenetic analysis and flow cytometry, and a core biopsy for bone marrow cellularity. If it is not possible to conduct cytogenetic analysis or flow cytometry on the bone marrow aspirate, then attempts should be made to carry out the tests on a blood sample. Full reports must be provided by the investigator for documentation on the Patient Safety database. These data will be recorded in eCRF.

